8.2 Pharmacokinetic (PK) Parameters

8.2.1 Part 1a (SAD)

For Part 1a, the following PK parameters will be calculated, whenever possible, by non-compartmental methods for ATH-399A:

Table 8.21-1: SAD Plasma PK Parameters

Parameter	Definition
AUC _{0-t}	area under the concentration-time curve from time zero until the last observed concentration
AUC _{0-inf}	area under the concentration-time curve from time zero to infinity (extrapolated)
C _{max}	maximum observed concentration
T _{max}	time when the maximum concentration is observed
t _{1/2 el}	terminal elimination half-life
λ _z	terminal elimination rate constant

This document is confidential.

Table 8.21-2: SAD Urine PK Parameters

Parameter	Definition
Ae_{0-t}	Cumulative urinary excretion from time zero to time t , calculated as the sum of the amounts excreted over each collection interval
R_{max}	Maximal rate of urinary excretion, calculated by dividing the amount of drug excreted in each collection interval by the time over which it was collected
T_{Rmax}	Time of maximal urinary excretion, calculated as the midpoint of the collection interval during which R_{max} occurred
Cl_R	Renal clearance, calculated as Ae_{0-t} / AUC_{0-t}

8.2.2 Part 1b (Food Effect)

For Part 1b, the PK parameters presented in [Table 8.2.2-1](#) will be calculated, whenever possible, by non-compartmental methods for ATH-399A.

Table 8.2.2-1: Food Effect Plasma PK Parameters

Parameter	Definition
AUC_{0-t}	Area under the concentration-time curve from time zero until the last observed concentration
AUC_{0-inf}	Area under the concentration-time curve from time zero to infinity (extrapolated)
C_{max}	Maximum observed concentration
T_{max}	Time when the maximum concentration is observed
$t_{1/2 el}$	Terminal elimination half-life
λ_z	Terminal elimination rate constant

8.2.3 Part 2 (MAD)

For Part 2, the PK parameters presented in [Table 8.2.3-1](#) will be calculated, whenever possible, by non-compartmental methods for ATH-399A:

Table 8.2.3-1: MAD Plasma PK Parameters

Parameter	Definition
AUC_{0-24}	Area under the concentration-time curve from time zero to 24-hours post-dose
C_{max}	Maximum observed concentration
C_{min}	Minimum observed concentration
C_{avg}	Average observed concentration
T_{max}	Time when the maximum concentration is observed
$AUC_{0-\tau}$	Area under the concentration-time curve, for one dosing interval (τ) at steady state. In this study, $\tau = 24$ hours (AUC_{0-24})
AUC_{0-t}	Area under the concentration-time curve from time zero until the last observed concentration
AUC_{0-inf}	Area under the concentration-time curve from time zero to infinity (extrapolated)
$T_{max ss}$	Time when the maximum concentration is observed at steady-state

This document is confidential.

Parameter	Definition
$C_{max\ ss}$	Maximum observed concentration at steady state
$t_{1/2\ el}$	Terminal elimination half-life
λ_z	Terminal elimination rate constant
AR	Accumulation ratio

Note: λ_z will be the negative of the estimated slope of the linear regression of the ln-transformed concentration versus time profile in the terminal elimination phase. The Best-fit method, in Phoenix WinNonlin, will be used to calculate the λ_z from at least 3 concentration data points excluding the C_{max} . Rsq adjusted, the goodness of fit statistic for the terminal elimination phase, adjusted for the number of points used in the estimation of λ_z must be ≥ 0.8 . If the λ_z cannot be measured (e.g.: fewer than 3 non-zero concentrations in the terminal elimination phase or Rsq adjusted < 0.8), the PK parameters derived from λ_z (AUC_{0-inf} , $t_{1/2\ el}$, Cl/F , V_z/F , and $V_{z\ ss}/F$) will be presented in the listing with a flag and excluded from descriptive statistics. The timepoint where ln-linear λ_z calculation begins (λ_z Lower) and the actual sampling time of the last measurable concentration used to estimate the λ_z (λ_z Upper), as well as the Rsq adjusted for the ln-linear regression for the calculation of the elimination rate constant will be reported.

Note: If the Residual area is more than 20%, the individual result should be flagged as well as all parameters depending on AUC_{0-inf} . All the derived parameters (i.e., AUC_{0-inf} , $t_{1/2\ el}$, Cl/F , and V_z/F) will be flagged accordingly.

For Part 2, plasma concentration observed before treatment administrations (C_{trough}) and during repeated dosing (Day 9, Day 10, Day 11, and Day 12) will also be presented.

Area under the concentration-time curve (AUC) parameters will be calculated using the linear up log down trapezoidal method, where the linear trapezoidal rule is used any time the concentration data are increasing and the logarithmic trapezoidal rule is used any time that the concentration data are decreasing.

8.3 Assessment of Dose Proportionality

For Part 1a, the power model approach will be performed on AUC_{0-t} , AUC_{0-inf} , and C_{max} data to assess the dose proportionality. For Part 2, the power model approach will be performed on C_{max} , AUC_{0-t} , $C_{max\ ss}$, $C_{min\ ss}$, AUC_{0-t} , and AUC_{0-inf} data to assess the dose proportionality.

The power model will include the PK parameter as the response variable and dose (mg) as the explanatory variable. For this model, the variable dose will be treated as a continuous variable. All treatments will be considered for the analysis (a minimum of three different treatments are required in order to conduct the analysis).

The form of the model is as follows:

PK Parameter = $e^\alpha \times Dose^\beta \times e^\epsilon$, where Dose ≥ 0 , and e^ϵ represents the associated error.

Thus, perfect dose proportionality is met when $\beta=1$ (ignoring error). This becomes a linear relationship following a natural-log transformation, to which a linear regression will be fit by ordinary least squares (OLS):

$\ln(\text{PK Parameter}) = \alpha + \beta \times \ln(\text{Dose}) + \epsilon$ where Dose > 0 , and ϵ represents the associated error.

This document is confidential.

The estimate of β together with a 90% confidence interval (CI) will be provided (for each PK parameter model), and this will be used to quantify dose proportionality. The following criterion may be used for exploratory dose proportionality evaluations: If the (two-sided) 90% CI for β is wholly contained within the interval, $[1+\ln(0.5)/\ln(\rho), 1+\ln(2)/\ln(\rho)]$, then dose proportionality is suggested across the investigated dose range.^a Here, ρ is defined as the ratio of the highest to lowest dose. This interval criterion will be reported along with the corresponding 90% CI estimate for β (presented to three decimal places).

The SAS code for the analysis model will follow the format below (using the Mixed Procedure to fit the linear regression). The input variables, datasets, and labels are depicted in italicized red text and have been given generic names.

```
proc mixed data=dataset order=data;
  model ln_pk_parameter = ln_dose / solution;
  estimate 'Beta Estimate' ln_dose 1 / cl alpha=0.1;
  ods output estimates =estimates;
run;
```

The PK parameter values estimated from the power model will be plotted against dose. This plot will also include individual participant values and mean \pm SD (separately by treatment or dose level).

For Part 1a, an analysis of variance (ANOVA) will be performed on the untransformed T_{max} , $t_{1/2 el}$, and λ_z data. For Part 2, an ANOVA will also be performed on the untransformed T_{max} , $T_{max ss}$, $t_{1/2 el}$, and λ_z data. The SAS output for each model will be provided in listings.

The SAS code for the analysis model will follow the format below (using the Mixed Procedure to fit the linear regression). The input variables, datasets, and labels are depicted in italicized red text and have been given generic names.

```
proc mixed data=dataset order=data;
  class dose;
  model pk_parameter = dose;
  lsmeans dose;
  ods output estimates =estimates;
run;
```

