Participants will be admitted to the clinical unit on the day before study drug administration (Day -1) for baseline assessments, and to confirm eligibility. Participants will be dosed in the fasted state and will be required to fast for a minimum of 10 hours prior to dosing and 4 hours following dosing. Except for water given with the study drug, no fluids will be allowed from 1 hour before dosing until 1 hour after dosing. Participants in Study Part 1a will stay in the clinical unit for 4 days (3 nights), from Day -1 until Day 3. Blood samples for PK analysis for Cohorts 1, 2, and 3 will be collected pre-dose and at specified time points up to Day 3 (48 hours) post-dose and blood samples for PK analysis for Cohorts 4 and 5 will be collected pre-dose and at specified time points up to Day 5 (96 hours) post-dose. Urine samples for PK analysis will be collected from pre-dose and during specified time intervals up to Day 3 (48 hours post-dose). PK blood samples for Cohorts 4 and 5 will be collected at outpatient visits on Day 4 (72 hours post-dose) and Day 5 (96 hours post-dose). All participants in each cohort will return for a follow-up visit on Day 8 (between Day 8 and Day 11).

Physical and neurological examinations, safety labs (including drug screen, cotinine test, and alcohol breath test), vital signs, ECG, and telemetry will be performed at specified time points. AEs will be recorded throughout the study. For details regarding the timing of specific procedures, see [Table 1](#).

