Visit Day	Timepoint	Part 1a	Part 1b	Part 2
Day 1 of each Period/Cohort	Pre-dose (within 2 hours of dosing)	X	X	X
	0.25 hours (± 2 min) post-Day 1 dose	X	X	X
	0.5 hours (± 2 min) post-Day 1 dose	X	X	X
	1 hour (± 5 min) post-Day 1 dose	X	X	X
	1.5 hour (± 5 min) post-Day 1 dose	X	X	X
	2 hours (± 5 min) post-Day 1 dose	X	X	X
	3 hours (± 10 min) post-Day 1 dose	X	X	X
	4 hours (± 10 min) post-Day 1 dose	X	X	X
	6 hours (± 10 min) post-Day 1 dose	X	X	X
	8 hours (± 10 min) post-Day 1 dose	X	X	X
	12 hours (± 10 min) post-Day 1 dose	X	X	X
	16 hours (± 30 min) post-Day 1 dose	X	X	X
Day 2 of each Period/Cohort	24 hours (± 30 min) post-Day 1 dose	X	X	X
	36 hours (± 30 min) post-Day 1 dose	X	X	X
Day 3 of each Period/Cohort	48 hours (± 30 min) post-Day 1 dose	X	X	
Day 4 of each period	72 hours (± 1 hour) post-Day 1 dose (outpatient visit)	X (Cohorts 4 and 5 only)	X	
Day 5 of each period	96 hours (± 1 hour) post-Day 1 dose (outpatient visit)	X (Cohorts 4 and 5 only)	X	

Visit Day	Timepoint	Part 1a	Part 1b	Part 2
Day 9 of each Cohort	Pre-dose (within 2 hours of dosing)			X
Day 10 of each Cohort	Pre-dose (within 2 hours of dosing)			X
Day 11 of each Cohort	Pre-dose (within 2 hours of dosing)			X
Day 12 of each Cohort	Pre-dose (within 2 hours of dosing)			X
	0.25 hours (± 2 min) post-Day 12 dose			X
	0.5 hours (± 2 min) post-Day 12 dose			X
	1 hour (± 5 min) post-Day 12 dose			X
	1.5 hour (± 5 min) post-Day 12 dose			X
	2 hours (± 5 min) post-Day 12 dose			X
	3 hours (± 10 min) post-Day 12 dose			X
	4 hours (± 10 min) post-Day 12 dose			X
	6 hours (± 10 min) post-Day 12 dose			X
	8 hours (± 10 min) post-Day 12 dose			X
	12 hours (± 10 min) post-Day 12 dose			X
	16 hours (± 30 min) post-Day 12 dose			X
Day 13 of each Cohort	24 hours (± 30 min) post-Day 12 dose			X
	36 hours (± 30 min) post-Day 12 dose			X
Day 15 of each Cohort	72 hours (± 1 hour) post-Day 12 dose			X
Day 16 of each Cohort	96 hours (± 1 hour) post-Day 12 dose			X

An additional aliquot may be collected at each time point and stored for future evaluation of ATH-399A metabolites. Any blood samples drawn beyond the specified window period will be noted as early or late draws and will be recorded appropriately as a protocol deviation. A comment and explanation should be provided in the source documents. The exact collection time will be recorded in the source documents.

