11.8.2 Urine Pharmacokinetics

In Part 1a, urine samples will be collected for analysis of ATH-399A concentrations and identification of metabolites at pre-dose, and at the following time intervals: 0-4 hours, 4-8 hours, 8-12 hours, 12-24 hours, and 24-48 hours post-dose.

If a participant cannot void their bladder within 30 minutes before dosing, a urine sample from an earlier morning urine collection may be used as the pre-dose sample. Voids that occur within the time interval will be pooled, and participants will be asked to void their bladder within 30 minutes before the end of each collection interval, so that each new interval will begin with an empty bladder. Any urine voided by participants at the intersection (within 10 minutes) of two intervals will be included in the earlier sample. Any urine voided by participants but not collected will be documented. If a participant is unable to void at the end of a collection interval, the unsuccessful attempt will be documented.

Refer to the AMIS for the collection, processing, and shipping of urine samples.

For Part 1a, the following PK parameters will be calculated for [ATH-399A and metabolite(s), if applicable] urine concentrations:

- Ae_{0-t} : Cumulative urinary excretion from time zero to time t , calculated as the sum of the amounts excreted over each collection interval
- R_{max} : Maximal rate of urinary excretion, calculated by dividing the amount of drug excreted in each collection interval by the time over which it was collected
- T_{Rmax} : Time of maximal urinary excretion, calculated as the midpoint of the collection interval during which R_{max} occurred
- Cl_R : Renal clearance, calculated as Ae_{0-t}/AUC_{0-t}

Additional PK parameters may be calculated.

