8.1 Data Presentation

PK concentrations will be listed and summarized by nominal sampling time and treatment. For all PK analyses, concentration values below the quantification limit (BLQ) that occur before the first measurable concentration of the study drug will be set to “0.00”; BLQ values that occur after first measurable concentration will be set to “missing”. No imputations will be made on BLQ concentrations.

Invalid concentration values (due to bioanalytical or clinical issue) that occur prior to dosing will be replaced by “0.00”. Invalid concentration values that occur after dosing will be set to “missing” for tabulation, graphical representation, and calculation purposes.

The actual clock time for dosing and the actual clock time for each PK sample collection will be recorded. For all sampling times, the actual sampling duration will be calculated as the difference between the sample collection actual clock time and the actual clock time of dosing. The actual post-dose sampling times, expressed in hours and rounded off to three decimal places, will be used to calculate the PK parameters. Pre-dose sampling times will always be reported as zero (0.000), regardless of the time difference. Nominal sampling times will be used in concentration tables and mean graphs, while actual sampling times for post-dose samples will be used in the individual graphs. Actual sampling times for post-dose samples also will be used for PK parameter derivation, unless the actual sampling time is missing, in which case, the nominal time will be used.

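### Part 1a AUC0-t covers unequal time windows across doses, which can raise the power-model slope and leave renal clearance unmatched to its 48 h urine collection

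*SAP*

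**What the plan says.** - **Plasma sampling.** Protocol 7.1.1 ends it at 48 h for Cohorts 1 to 3 (5, 10, 20 mg). Samples "for Cohorts 4 and 5 will be collected pre-dose and at specified time points up to Day 5 (96 hours) post-dose". Table 6 in Protocol 11.8.1 marks the 72 h and 96 h rows "X (Cohorts 4 and 5 only)".
- **Urine sampling.** Protocol 11.8.2 ends collection at 48 h in every cohort; the last intervals are "8-12 hours, 12-24 hours, and 24-48 hours post-dose".
- **AUC0-t.** SAP 8.2.1 defines it as the "area under the concentration-time curve from time zero until the last observed concentration". SAP 8.1 adds that "BLQ values that occur after first measurable concentration will be set to" missing, so the area stops at the last measurable sample.
- **Cl_R.** SAP 8.2.1 and Protocol 11.8.2 both define it as Ae0-t/AUC0-t, with Ae0-t "calculated as the sum of the amounts excreted over each collection interval".
- **Dose proportionality.** SAP 8.3: "For Part 1a, the power model approach will be performed on AUC_{0-t", AUC0-inf and Cmax. It is one least-squares line of ln(parameter) on ln(dose) over all doses. The 90% CI for the slope may be compared, as an exploratory criterion, with an interval set by the dose ratio. Protocol 12.5 names the same three parameters.

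Neither document lists a common-window area for Part 1a, or says which AUC carries the conclusion if AUC0-t and AUC0-inf disagree.

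**The concern.** The power model takes AUC0-t as the same quantity at every dose, and two features of the plan prevent that. The schedule follows the two highest doses twice as long. The BLQ rule also ends the area earlier where concentrations are lower. A drug with exactly proportional exposure could therefore show a slope above 1.

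Cl_R has a related problem. If plasma is quantifiable beyond 48 h, Cl_R at 40 and 80 mg divides a 48 h amount by a longer area and comes out too low. If plasma turns BLQ before 48 h while urine is still measurable, Cl_R at low doses comes out too high. Either way, Cl_R could appear to fall with dose because of sampling and assay limits and not because of the drug.

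**Working it through.** **Inputs from the documents.** Doses 5, 10, 20, 40, 80 mg; 6 active participants per dose (30 in all); windows 48/48/48/96/96 h; urine to 48 h. SAP 8.3 interval with dose ratio 80/5 = 16: 1 + ln(0.5)/ln(16) = 0.75 to 1 + ln(2)/ln(16) = 1.25, a tolerance of 0.25 either side of 1.

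**Assumptions.** Half-life, LLOQ and between-participant CV are not given. Protocol 9.7 treats 96 h as enough to reach steady state in Part 2. Read as 5 or 4 half-lives, that suggests at most 96/5 = 19.2 h or 96/4 = 24 h. This is an inferred ceiling, not an expected value. The half-lives used are 8, 12, 19.2 and 24 h.

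**Direction.** With a common profile shape, a higher dose is sampled for as long or longer and stays above the LLOQ for as long or longer. The captured share of AUC0-inf cannot fall as dose rises, so both effects raise the slope or leave it alone.

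**Schedule alone (quantifiable to the last sample).** Share captured by time T: F(T) = 1 − 2^(−T/half-life). The centred ln(dose) values are (−2, −1, 0, 1, 2) × ln 2, so Sxx = 10(ln 2)². A step s = ln(F96/F48) at the top two doses shifts the slope by 3s/(10 ln 2). The Cl_R ratio at those doses is F48/F96.

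| Half-life | F48 | F96 | s | Slope shift | Cl_R at 40, 80 mg |
|---|---|---|---|---|---|
| 8 h | 0.984 | 1.000 | 0.016 | +0.007 | 1.5% low |
| 12 h | 0.938 | 0.996 | 0.061 | +0.026 | 5.9% low |
| 19.2 h | 0.823 | 0.969 | 0.163 | +0.070 | 15% low |
| 24 h | 0.750 | 0.938 | 0.223 | +0.097 | 20% low |

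By simulation with true slope 1 and CV 30%, the chance of meeting the criterion is 99.5% with no mismatch and 99.5%, 99.0%, 93.8% and 85.6% at the four half-lives. At CV 40% it falls from 92% to 78% (19.2 h) and 67% (24 h).

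**Schedule and BLQ together.** Typical participant, protocol sampling grid, one-compartment oral curve with absorption rate 1.5/h (assumed), linear-up log-down area, SAP BLQ rule. AUC0-t slope, by LLOQ as a share of the 5 mg Cmax:

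| Half-life | 1% | 5% | 10% | 20% | 30% | 32% |
|---|---|---|---|---|---|---|
| 8 h | 1.006 | 1.014 | 1.041 | 1.098 | 1.098 | 1.160 |
| 12 h | 1.027 | 1.026 | 1.043 | 1.093 | 1.168 | 1.168 |
| 19.2 h | 1.072 | 1.072 | 1.072 | 1.109 | 1.103 | 1.171 |

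The slope is thus about 1.01 to 1.07 for an LLOQ of 1% to 10%, 1.09 to 1.11 at 20%, and 1.10 to 1.17 at about 30%. The values jump because the last quantifiable sample moves between scheduled times. With absorption rate 1/h, the 19.2 h value at 20% is 1.074 instead of 1.109.

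**Cl_R at low doses.** At an LLOQ of 10%, the last quantifiable 5 mg sample is at 24 h (half-life 8 h) or 36 h (12 h). With urine measured to 48 h, Cl_R is too high by F48/F24 = 0.984/0.875, or 12.5%, and by F48/F36 = 0.9375/0.875, or 7.1%.

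**Urine can go the other way.** If the 24-48 h urine is lost at a half-life of 8 h, the amount stops at 24 h. Dividing it by a 48 h area gives 0.875/0.984 = 0.889, which is 11% low.

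**The case against.** The best defence is that proportionality is already covered. AUC0-inf and Cmax are in the same model. In simulations with participant variation, AUC0-inf gave almost the same slope as a 48 h area (for example 0.979 against 0.981, and 0.999 against 0.999). This stands, and it is why AUC0-inf should lead. It does not help Cl_R, which uses AUC0-t. It also weakens where lambda-z cannot be estimated.

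Other mitigations are real but partial. A residual area above 20% is flagged. The 48 h cohorts reach that level at a half-life above 48 × ln 2/ln 5 = 20.7 h, but the flag attaches to AUC0-inf and its dependants, not to AUC0-t. Protocol 13.1.5.1 lets the SRC change the PK collection interval by up to 48 h. That could remove the difference or widen it, and nothing requires the windows to be made equal. The shared subscript t might be read as one window for Ae and AUC, but neither document says so.

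A reader might infer that Part 1a will report strong false supra-proportionality. Simulated mean slopes of about 1.15 to 1.32, and Cl_R 46% to 55% high at 5 mg, can be produced. They need an LLOQ of about 30% to 56% of the typical 5 mg Cmax, and the documents give no LLOQ to support that. Nor is it assured that Cl_R is too high at low doses, because urine BLQ would shorten the numerator as well.

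**Conclusion.** The point holds in a limited form: minor to should-fix. The unequal windows, the last-observed definition and the unmatched Cl_R are all in the text. The upward direction of the slope effect follows without knowing the PK values, given a proportional drug with a common profile shape. The size does not. It is negligible at a half-life near 8 h with a sensitive assay. It reaches about 0.07 to 0.10 on the slope, and 15% to 20% on Cl_R at 40 and 80 mg, at the 19.2 to 24 h inferred ceiling.

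Sampling longer at higher doses is not itself an error; using AUC0-t across those windows without a matched interval is. A reader might also infer a threat to dose escalation or to the primary results. The documents do not support that: Cmax and the AUC0-24 limit are unaffected by the 48 h and 96 h difference, PK is secondary, the study is not powered, the criterion is exploratory, and Cl_R is not among the endpoints in SAP 4.1.2.

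**What to change.** 1. **SAP 8.2.1, Cl_R.** Define it as Ae0-T/AUC0-T over one matched interval. Use T = 48 h in every cohort where the plasma area to 48 h is observed, or can be completed with a lambda-z that meets the SAP 8.2.3 note, as a named exception to SAP 6.4. Otherwise use, for that participant, the last urine interval end covered by quantifiable plasma, and report T. State how a BLQ or missing urine interval is handled, and apply the same T to numerator and denominator.
2. **SAP 8.3.** Base the Part 1a AUC proportionality statement on AUC0-inf, with AUC0-48 as a matched-window check. Keep AUC0-t as supportive, with a note on the unequal windows, so that Protocol 12.5 is still met. Report the number of participants per dose with no AUC0-inf or AUC0-48. Cutting at 48 h without completing BLQ tails is not enough: with an absorption rate of 1/h, a half-life of 8 h and an LLOQ of 20% of the 5 mg Cmax, the slope stays at 1.102.
3. **Scope and record.** Say that the lambda-z and residual-area notes, now placed under Part 2, apply to Part 1a. Record the changes in SAP section 11.

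**Cost.** One more partial-area parameter, which Protocol 11.8.2 already allows ("Additional PK parameters may be calculated"); a departure from the protocol's Cl_R formula; and some low-dose values that may not be calculable. In the harshest simulated case (19.2 h, 80 mg just quantifiable at 96 h), about 2.8 of 6 participants at 5 mg had no AUC0-48. No new samples, visits or participants are needed.
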